## **7.2 Serious adverse events**

### **7.2.1 Definition of SAE**

An SAE is defined as any adverse event [appearance of (or worsening of any pre-existing)] undesirable sign(s), symptom(s) or medical condition(s) which meets any one of the following criteria:

- is fatal or life-threatening
- results in persistent or significant disability/incapacity
- constitutes a congenital anomaly/birth defect
- requires inpatient hospitalization or prolongation of existing hospitalization, unless hospitalization is for:
  - routine treatment or monitoring of the studied indication, not associated with any deterioration in condition (specify what this includes)
  - elective or pre-planned treatment for a pre-existing condition that is unrelated to the indication under study and has not worsened since signing the informed consent
  - treatment on an emergency outpatient basis for an event not fulfilling any of the definitions of a SAE given above and not resulting in hospital admission

- social reasons and respite care in the absence of any deterioration in the patient's general condition
- is medically significant, e.g. defined as an event that jeopardizes the patient or may require medical or surgical intervention.

All malignant neoplasms will be assessed as serious under “medically significant” if other seriousness criteria are not met.

Life-threatening in the context of a SAE refers to a reaction in which the patient was at risk of death at the time of the reaction; it does not refer to a reaction that hypothetically might have caused death if it were more severe (see Annex IV, ICH-E2D Guideline).

Medical and scientific judgment should be exercised in deciding whether other situations should be considered serious reactions, such as important medical events that might not be immediately life threatening or result in death or hospitalization but might jeopardize the patient or might require intervention to prevent one of the other outcomes listed above. Examples of such events are intensive treatment in an emergency room or at home for allergic bronchospasm, blood dyscrasias or convulsions that do not result in hospitalization or development of dependency or abuse (see Annex IV, ICH-E2D Guideline).

All diagnosed cases of ONJ should be considered as “medically significant” irrespective of whether the event meets the definition of “Serious Adverse Event” under current health authority guidelines. These cases are therefore reported to Novartis Drug Safety and Epidemiology as well as local health authorities under the guideline of SAE reporting.

Any suspected transmission via a medicinal product of an infectious agent is also considered a serious adverse event.

### **7.2.2 SAE reporting**

To ensure patient safety, every SAE, regardless of causality, occurring after the patient has provided informed consent and until 30 days after the last study visit must be reported to Novartis within 24 hours of learning of its occurrence. Any SAEs experienced after the 30 day period after the last study visit should only be reported to Novartis if the investigator suspects a causal relationship to study treatment.

All follow-up information for the SAE including information on complications, progression of the initial SAE and recurrent episodes must be reported as follow-up to the original episode within 24 hours of the investigator receiving the follow-up information. An SAE occurring at a different time interval or otherwise considered completely unrelated to a previously reported one must be reported separately as a new event.

Information about all SAEs (*either initial or follow up information*) is collected and recorded on the paper Serious Adverse Event Report Form. The investigator must assess the relationship to *each specific component of study treatment (if study treatment consists of several components)* complete the SAE Report Form in English, and send the completed, signed form by fax within 24 hours after awareness of the SAE to the local Novartis Drug Safety and Epidemiology Department. The telephone and fax number of the contact persons in the local department of Drug Safety and Epidemiology, specific to the site, are listed in the investigator folder provided to each site. The original copy of the SAE Report Form and the

fax confirmation sheet must be kept with the case report form documentation at the study site. Follow-up information should be provided using a new paper SAE Report Form stating that this is a follow-up to a previously reported SAE

Follow-up information provided must describe whether the event has resolved or continues, if and how it was treated, whether the treatment code was broken or not and whether the patient continued or withdrew from study participation. Each re-occurrence, complication, or progression of the original event must be reported as a follow-up to that event regardless of when it occurs.

If the SAE is not previously documented in the Investigator’s Brochure or Package Insert (new occurrence) and is thought to be related to the study treatment a Drug Safety and Epidemiology Department associate may urgently require further information from the investigator for health authority reporting. Novartis may need to issue an Investigator Notification (IN) to inform all investigators involved in any study with the same study treatment that this SAE has been reported. Suspected Unexpected Serious Adverse Reactions (SUSARs) will be collected and reported to the competent authorities and relevant ethics committees in accordance with EU Guidance 2011/C 172/01 or as per national regulatory requirements in participating countries.

### 7.3 Reporting of study treatment errors including misuse/abuse

Medication errors are unintentional errors in the prescribing, dispensing, administration or monitoring of a medicine while under the control of a healthcare professional, patient or consumer (EMA definition).

Misuse refers to situations where the medicinal product is intentionally and inappropriately used not in accordance with the protocol.

Abuse corresponds to the persistent or sporadic, intentional excessive use of a medicinal product, which is accompanied by harmful physical or psychological effects.

Study treatment errors and uses outside of what is foreseen in the protocol will be collected in the DAR (dose administration record) eCRF irrespective of whether or not associated with an AE/SAE and reported to Safety only if associated with an SAE. Misuse or abuse will be collected and reported in the safety database irrespective of it being associated with an AE/SAE.

Treatment error type	Document in Dose Administration (DAR) eCRF (Yes/No)	Document in AE eCRF	Complete SAE form
Unintentional study treatment error	Yes	Only if associated with an AE	Only if associated with an SAE
Misuse/Abuse	Yes	Yes,	Yes, even if not associated with a SAE

### 7.4 Pregnancy reporting

There are no adequate data on the use of zoledronic acid in pregnant women. Studies in animals with zoledronic acid have shown reproductive toxicological effects including

malformations. Teratology studies were performed in two species, both via subcutaneous administration. Teratogenicity was observed in rats at doses greater than or equal to 0.2 mg/kg and was manifested by external, visceral and skeletal malformations. Dystocia was observed at the lowest dose (0.01 mg/kg body weight) tested in rats. No teratological or embryo/fetal effects were observed in rabbits, although maternal toxicity was marked at 0.1 mg/kg due to decreased calcium levels. No risks in males were identified. The potential risk for humans is unknown. Despite this theoretical risk, there have been no human reports to date of an adverse effect of bisphosphonates when administered either pre-conception or during pregnancy. This appears to stem from the fact that the amount of bisphosphonate that is mobilized from the skeleton is clinically insignificant is supported by numerous human reports of bisphosphonate administration pre-conception/during pregnancy and newborn outcomes (Levy 2009 and Djokanovic 2008).

[For sites where additional safeguards are required only e.g. UK, Italy, Germany, Sweden & etc.: If the patient is a female of child bearing potential, the investigator must ensure that patient and parent(s)/guardian(s):

- understands the theoretical teratogenic risk
- understands the need for follow-up (e.g. pregnancy testing) on a regular basis
- has used at least one and preferably two methods of effective contraception including a barrier method for at least 2 months prior to screening and is continuing to use effective contraception throughout the duration of the trial and for at least 1 year after the end of the trial
- understands and accepts the need for effective contraception
- follows the advice on effective contraception, even if patient has amenorrhea
- is capable of complying with effective contraceptive measures
- is informed and understands the potential consequences of pregnancy and the need to rapidly consult if there is a risk of pregnancy
- has acknowledged the precautions associated with the use of zoledronic acid.]

To ensure patient safety, each pregnancy occurring after signing the informed consent must be reported to Novartis within 24 hours of learning of its occurrence. The pregnancy should be followed up to determine outcome, including spontaneous or voluntary termination, details of the birth, and the presence or absence of any birth defects, congenital abnormalities, or maternal and/or newborn complications.

Pregnancy must be recorded on the Pharmacovigilance Pregnancy Form and reported by the investigator to the local Novartis Drug Safety and Epidemiology Department. Pregnancy follow-up should be recorded on the same form and should include an assessment of the possible relationship to the study treatment.

Any SAE experienced during the pregnancy and unrelated to the pregnancy must be reported on a SAE form.

## **8 Data review and database management**

### **8.1 Site monitoring**

Before study initiation, either at a site initiation visit or at an investigator's meeting, a Novartis representative will review the protocol and CRFs with the investigators and their staff. During the study, Novartis employs several methods of ensuring protocol and GCP compliance and the quality/integrity of the sites' data. The field monitor will visit the site to check the completeness of patient records, the accuracy of entries on the (e)CRFs, the adherence to the protocol and to Good Clinical Practice, the progress of enrollment, and to ensure that study treatment is being stored, dispensed, and accounted for according to specifications. Key study personnel must be available to assist the field monitor during these visits. Continuous remote monitoring of each site's data may be performed by a centralized Novartis CRA organization. Additionally, a central analytics organization may analyze data & identify risks & trends for site operational parameters, and provide reports to Novartis Clinical Teams to assist with trial oversight.

The investigator must maintain source documents for each patient in the study, consisting of case and visit notes (hospital or clinic medical records) containing demographic and medical information, laboratory data, and the results of any other tests or assessments. All information on CRFs must be traceable to these source documents in the patient's file. Data not requiring a separate written record will be defined before study start and will be recorded directly on the CRFs. The investigator must also keep the original informed consent form signed by the patient or parent(s)/guardian(s) [a signed copy is given to the patient or parent(s)/guardian(s)].

The investigator must give the monitor access to all relevant source documents to confirm their consistency with the CRF entries. Novartis monitoring standards require full verification for the presence of informed consent, adherence to the inclusion/exclusion criteria, documentation of SAEs, and of data that will be used for all primary variables. Additional checks of consistency of the source data with the CRFs are performed according to the study-specific monitoring plan. No information in source documents about the identity of the patients will be disclosed.

### **8.2 Data collection**

Designated investigator staff will enter the data required by the protocol into the Oracle Clinical/Remote Data Capture (OC/RDC) system. Designated investigator site staff will not be given access to the system until they have been trained.

Automatic validation procedures within the system check for data discrepancies during and after data entry and, by generating appropriate error messages, allow the data to be confirmed or corrected online by the designated investigator site staff. The Investigator must certify that the data entered into the electronic Case Report Forms are complete and accurate. After database lock, the investigator will receive copies of the patient data for archiving at the investigational site.

### **8.3 Database management and quality control**

Novartis staff (or CRO working on behalf of Novartis) review the data entered into the CRFs by investigational staff for completeness and accuracy and instruct the site personnel to make any required corrections or additions. Queries are sent to the investigational site using an electronic data query. Designated investigator site staff is required to respond to the query and confirm or correct the data.

Concomitant medications entered into the database will be coded using the WHO Drug Reference List, which employs the Anatomical Therapeutic Chemical classification system. Concomitant procedures, non-drug therapies and adverse events will be coded using the Medical dictionary for regulatory activities (MedDRA) terminology.

Laboratory samples will be processed centrally and the results will be sent electronically to Novartis (or a designated CRO).

Randomization codes and data about all study drug(s) dispensed to the patient and all dosage changes will be tracked using an Interactive Response Technology (IRT). The system will be supplied by a vendor, who will also manage the database. The database will be sent electronically to Novartis (or a designated CRO).

DXA and X-ray data will be processed centrally through a central imaging vendor and the results will be sent electronically to Novartis.

Bone-marker analysis will be processed centrally through a central laboratory vendor and the results will be sent electronically to Novartis.

Each occurrence of a code break via IRT will be reported to the clinical team and monitor. The code break functionality will remain available until study shut down or upon request of Novartis.

The occurrence of relevant protocol deviations will be determined. After these actions have been completed and the database has been declared to be complete and accurate, it will be locked and the treatment codes will be unblinded and made available for data analysis. Any changes to the database after that time can only be made after written agreement by Novartis Development management.

### **8.4 Data Monitoring Committee**

A Data Monitoring Committee (DMC) will be implemented to safeguard patient safety. All members will be independent from the sponsor and study investigators. The DMC will conduct regularly scheduled meetings to review study progress and any potential emerging safety signals in the study population.

## **9 Data analysis**

The analysis will be conducted on all subject data at the time the trial ends. Any data analysis carried out independently by the investigator should be submitted to Novartis before publication or presentation.

## **9.1 Analysis sets**

### **9.1.1 Intention-to-treat (ITT) population**

The ITT population will consist of all patients randomized. Following the ITT principle, patients will be analyzed according to the treatment they were assigned to at randomization.

### **9.1.2 Modified Intention-to-treat (MITT) population**

The MITT population will consist of all patients in the ITT population who have an evaluable baseline assessment for the endpoint of interest.

Patients will be included in the MITT population for the analysis of the primary efficacy endpoint (change in lumbar spine Z-score at Month 12 relative to baseline) if their DXA assessments includes baseline and at least one post-baseline LS-BMD score.

According to the ITT principle, patients will be analyzed with respect to the treatment to which they were randomized.

### **9.1.3 Per-protocol (PP) population**

The PP will include all patients in the ITT population who do not have any major protocol deviations. Prior to unblinding, the Clinical Trial Team and Trial Statistician will identify the major protocol deviations that will exclude patients from the PP population.

### **9.1.4 Safety population**

The Safety Population will consist of all patients that have been exposed to at least one infusion of study drug. Patients will be analyzed according to treatment received.

## **9.2 Patient demographics and other baseline characteristics**

Appropriate summary statistics for the demographic and other baseline characteristics variables will be provided for the ITT and MITT populations. In addition, the baseline comparability between treatment groups will be evaluated for demographic and other baseline characteristics variables. Categorical variables will be evaluated using Fisher's exact test, and the continuous variables will be evaluated using a Wilcoxon rank-sum test.

Note that these tests of comparability are performed for descriptive purpose only, and will not be considered to define any formal basis for determining factors which should be included in statistical analysis models. However, when these tests yield significant results they can be used as extra information in interpreting any treatment-by-factor interactions that are observed in the sensitivity analyses performed on the primary and secondary efficacy variables.

## **9.3 Treatments**

### **9.3.1 Study drug and compliance**

Descriptive statistics will be provided by treatment group for duration of infusion and volume of infusion.

Summary statistics will be provided for the percentage of calcium taken post-infusion and the duration of exposure by treatment group.

### 9.3.2 Concomitant therapy

Concomitant medications will be coded using the WHO Drug Reference List that employs the Anatomical Therapeutic Chemical classification system. Summary tables will be provided that present the number and percent of patients receiving those medications by preferred term and treatment after start of study drug administration. The medications will be sorted in decreasing order of frequency with respect to usage in the zoledronic acid group.

Descriptive summary statistics (mean, median, standard deviation, minimum, maximum) will be provided for the dose and duration of use of glucocorticoids by treatment group at baseline and during the 12-month double-blind period. Descriptive summary statistics (mean, median, standard deviation, minimum, maximum) will also be provided for the duration of exposure to glucocorticoid treatment between randomization and the end of double-blind treatment. The number and percentage of patients receiving different types of glucocorticoid therapy will be presented by preferred term and treatment group.

Usage of calcium and vitamin D will be summarized by treatment group with respect to the forms of calcium and vitamin D taken.

## 9.4 Analysis of the primary variable

### 9.4.1 Variable

The primary efficacy variable will be the change in LS-BMD Z-score at Month 12 relative to baseline, in patients treated with twice yearly i.v. ZOL compared to patients treated with placebo. It is derived as (LS-BMD Z-score at Month 12 – LS-BMD Z-score at baseline).

### 9.4.2 Statistical model, hypothesis, and method of analysis

The primary efficacy objective is to demonstrate superiority with respect to the change in LS-BMD Z-score at Month 12 relative to baseline in patients treated with zoledronic acid compared to patients receiving placebo.

Let  $\mu_Z$  and  $\mu_P$  be the population mean of the change in LS-BMD Z-score at Month 12 relative to baseline for patients treated with ZOL and patients receiving placebo, respectively. The null hypothesis of no difference between treatment groups ( $H_0 : \mu_Z = \mu_P$ ) will be tested against the alternative hypothesis that there is difference between treatment groups ( $H_A : \mu_Z \neq \mu_P$ ). The tests will be done at a nominal significance level of  $\alpha = 0.05$ .

The primary efficacy objective will be demonstrated by showing that the t test statistic,  $\frac{|d|}{SE}$ , is greater than  $t_{df,0.975}$  in the modified intent-to-treat population, where  $d$  and  $SE$  are the estimated treatment difference and the estimated standard error of  $d$  from an analysis of covariance (ANCOVA) model with treatment, pooled centers, underlying condition treated with glucocorticoids and baseline LS-BMD Z-score as explanatory variables,  $df$  is the associated degrees of freedom computed from the error term in the model, and  $t_{df,0.975}$  is the

97.5% quantile of the  $t$  distribution with  $df$  degree of freedom. The test and confidence intervals based on this test statistic are robust to the assumptions of normality and of equal variances when within-center treatment group sample size are equal, which is generally the case that treatment allocation is nearly equal within each center because of the manner in which the randomization is carried out. Nevertheless, the underlying assumption of normality and variance homogeneity for the primary analyses will be reviewed and tested by Shapiro's test and Levene's test, respectively, prior to unblinding the data. If the underlying assumption is violated, a transformation or non-parametric approach, such as van Elteren or Cochran-Mantel-Haenszel test (CMH2 from SAS procedure PROC FREQ) adjusted for center, will be applied to the data as appropriate for the hypothesis evaluated.

#### **9.4.3 Handling of missing values/censoring/discontinuations**

In the modified intent-to-treat population, last observation carried forward (LOCF) will be used to impute a value for LS-BMD Z-score at Month 12 for any patient who does not have a Month 12 assessment; however, if a patient prematurely discontinues from the study during the double-blind phase without providing any LS-BMD measurements at Month 6 or Month 12, then a zero percent change in LS-BMD will be assumed at Month 12.

Given that a pediatric population is being studied and patients are expected to experience bone growth during the study, an assumption of zero change over 12 months and LOCF from Month 6 measurements would be considered conservative.

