#### **9.4.4 Sensitivity analyses**

Confirmation of the result for the primary efficacy variable will be performed using the per-protocol population without imputation for missing data using the ANCOVA model applied for the primary efficacy analysis.

As another supportive analysis to the primary analysis, the change in LS-BMD Z-score at Month 12 relative to baseline will be compared using the analysis of covariance model with treatment, pooled centers, underlying condition treated with glucocorticoids, baseline LS-BMD Z-score and treatment-by-center interaction as explanatory variables to explore treatment-by-center interactions using the MITT population. If  $p < 0.1000$  for the treatment-by-center interaction test, then, in addition, further work will be done (tabular and/or graphical presentations) as necessary to look for a possible explanation to the differences observed across centers. Tabular and graphical presentations will also be presented as necessary to explain interactions if they exist for underlying condition and baseline pubertal status. Additional prognostic factors will be evaluated as necessary descriptively and in model fitting.

In addition, a responder analysis will be done by comparing the proportion of patients who increase their lumbar spine z-score at Month 12 in the ZOL group relative to the placebo group using the MITT population. Between-treatment differences will be evaluated using a logistic regression model with treatment, pooled centers, underlying condition treated with glucocorticoids and baseline LS-BMD Z-score as explanatory variable.

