## 9.8 Sample size calculation

The sample size is calculated to show superiority of zoledronic acid relative to placebo at Month 12.

The null hypothesis of no difference between treatment groups in the mean change in LS-BMD Z-score at Month 12 relative to baseline. In testing this hypothesis, it is assumed that the standard deviations for the two treatment groups is 0.93 under  $H_0$  and  $H_A$ . Based on a primary endpoint of the change in LS-BMD Z-score at 12 months relative to baseline assuming a 0.63 increase in LS-BMD Z-score over 12 months with zoledronic acid and no change in the LS-BMD Z-score in the placebo group and a common standard deviation of 0.93, 82 patients are required to show a significant increase in LS-BMD Z-score at the 0.05 level with 85% power. Adjusting for a dropout rate of 10%, approximately 46 patients per treatment group are required.

The amount of information from controlled trials in a pediatric GIO population is limited. The 0.63 increase in LS-BMD Z-score is based on the increase observed with pamidronate-treated children on chronic glucocorticoid therapy presented in (Acott et al 2005). The common standard deviation of 0.93 was estimated from the pamidronate-treated children and untreated control evaluated in (Acott et al 2005). This standard deviation is consistent with the estimate of the standard deviation obtained from the zoledronic acid group of pediatric osteogenesis imperfecta patients in Study CZOL446H2202. Therefore, it is inferred that the assumption of a 0.63 increase in LS-BMD Z-score over 12 months with ZOL is acceptable.

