Elteren or Cochran-Mantel-Haenszel test adjusted for center, will be applied to the data as appropriate for the hypothesis evaluated.

From the model, the treatment difference between zoledronic acid group vs. placebo group will be estimated and presented together with two-sided 95% confidence interval (CI). P-value will be rounded to the 4th decimal place. In the same table, the Least Squares means and standard errors for change from baseline in lumbar spine Z-score at Month 12 will be presented for each treatment group. Descriptive statistics will also be shown for baseline and Month 12 visits.

A plot will be generated for LS BMD Z-score over time.

Handling of missing values/censoring/discontinuations

In the MITT population, last observation carried forward (LOCF) will be used to impute a value for LS-BMD Z-score at Month 12 for any patient who does not have a Month 12 assessment; however, if a patient prematurely discontinues from the study during the double-blind phase without providing any LS-BMD measurements at Month 6 or Month 12, then a zero percent change in LS-BMD will be assumed at Month 12.

Given that a pediatric population is being studied and patients are expected to experience bone growth during the study, an assumption of zero change over 12 months and LOCF from Month 6 measurements would be considered conservative.

Supportive analyses

Confirmation of the result for the primary efficacy variable will be performed using the per-protocol population without imputation for missing data using the ANCOVA model applied for the primary efficacy analysis.

As another supportive analysis to the primary analysis, the homogeneity of treatment effects across centers will be evaluated by adding the treatment-by-center interaction term into the ANCOVA model employed in the primary efficacy analysis. If $p < 0.1000$ for the treatment-by-center interaction test, which indicates heterogeneous treatment effects across centers, then an additional table will be presented showing the ANCOVA model-based treatment comparisons for primary efficacy variable by each center. Furthermore, interactions between treatment and underlying condition, treatment and baseline tanner stage in pubic hair, treatment and baseline tanner stage in breast development within female population, and treatment and baseline tanner stage in genital stage within male population will be evaluated and presented in a similar way.

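### Carrying the last LS-BMD Z-score forward to Month 12 is called conservative because children grow, but growth does not support that for a Z-score, and no MITT analysis tests the imputation; at the planned 10% dropout the effect is small

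*Protocol*

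**What the plan says.** In the primary MITT analysis, "last observation carried forward (LOCF) will be used to impute a value for LS-BMD Z-score at Month 12" for any child without a Month 12 scan (SAP, Handling of missing values/censoring/discontinuations; same rule in Protocol 9.4.3). A child who leaves with no Month 6 or Month 12 measurement is given a zero percent change in LS-BMD. Both documents justify the two rules together. Bone growth is expected in a pediatric population, so "an assumption of zero change over 12 months and LOCF from Month 6 measurements would be considered conservative".

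Three other places bear on this:

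- The sample size assumes "no change in the LS-BMD Z-score in the placebo group" over the 12 months (Protocol 9.8).
- The primary result is to be confirmed "using the per-protocol population without imputation for missing data" (Protocol 9.4.4; the SAP says the same under Supportive analyses). This is the only analysis of the primary variable stated to be free of imputation.
- The MITT set for the primary endpoint requires a baseline and at least one post-baseline LS-BMD value (Protocol 9.1.2; SAP, MITT population and Appendix).

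**The concern.** The growth argument would concern raw bone density, which rises as a child grows. The endpoint is a change in Z-score, which Protocol 3.6 describes as a deviation from normal. A child growing as expected keeps the same Z-score, and Protocol 9.8 assumes exactly that for placebo. Protocol 6.5.6 even sets an alert for a fall beyond 0.5 from screening, so decline is foreseen. Growth would not settle the matter for raw density either: a trend common to both arms cancels when dropout is equal, and can push either way when it is not.

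Without that argument, the direction of the bias depends on what happens between the carried scan and Month 12, which the documents do not specify. This is the only confirmatory test. Its estimate blends earlier and Month 12 effects in proportion to dropout, and the ANCOVA treats carried values as observed. The one imputation-free analysis also changes the population, so a discrepancy could not be traced to LOCF.

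**Working it through.** **Inputs from the documents.** Test: the null "will be tested against the alternative hypothesis that there is difference between treatment groups" (Protocol 9.4.2), judged against the 97.5% t quantile, so two-sided 0.05. Design: "assuming a 0.63 increase in LS-BMD Z-score over 12 months with zoledronic acid and no change in the LS-BMD Z-score in the placebo group" (Protocol 9.8). The same section takes the SD of the change as 0.93 in each arm. Dropout 10%, 46 per arm.

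**The plan's own figure.** The protocol states that "82 patients are required to show a significant increase in LS-BMD Z-score at the 0.05 level with 85% power". Normal approximation: 2 × (1.960 + 1.036)² × 0.93² / 0.63² = 39.1, so 40 per arm. With the t distribution it is 41 per arm, 82 in all, power 85.8%. Then 82 / 0.90 = 91.1, rounded up to 92, or 46 per arm. The figure reproduces.

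**Standard error at 46 per arm.** 0.93 × √(2/46) = 0.194, ignoring covariates.

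**Bias formula.** Let p_Z and p_P be the shares carried forward in each arm, and s_Z and s_P the true mean Z-score change in those children from the carried scan to Month 12. Then

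bias in (zoledronic acid − placebo) = p_P·s_P − p_Z·s_Z.

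With equal dropout p this is −p × (widening of the difference after the carried scan). With unequal dropout, a common trend g adds g × (p_P − p_Z), of either sign.

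**Planned dropout, 10% in each arm, true Month 12 difference 0.63, placebo flat.** The Month 6 differences are assumptions.

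| Month 6 difference | LOCF estimate | Change |
|---|---|---|
| 0.315 (linear gain) | 0.63 − 0.10 × 0.315 = 0.599 | −5.0% |
| 0.40 | 0.63 − 0.10 × 0.23 = 0.607 | −4% |
| 0.63 (plateau) | 0.63 | none |
| 0.80 (early peak, then waning) | 0.63 + 0.10 × 0.17 = 0.647 | +2.7% |

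For the 0.40 row the shift is 0.023 / 0.194 = 0.12 standard errors.

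**Higher dropout (assumed), Month 6 difference 0.40.**

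- 20% per arm: 0.63 − 0.20 × 0.23 = 0.584 (−7%).
- 30% per arm: 0.63 − 0.30 × 0.23 = 0.561 (−11%).

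**No true Month 12 difference (assumed scenarios).**

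- Month 6 difference 0.30 that vanishes by Month 12, 20% dropout per arm: bias +0.20 × 0.30 = +0.06.
- Both arms at −0.2 at Month 6 and −0.4 at Month 12, dropout 25% on zoledronic acid and 5% on placebo: bias = 0.05 × (−0.2) − 0.25 × (−0.2) = +0.04.

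**Simulation.** 46 per arm, Month 12 SD 0.93; Month 6 SD 0.75 and correlation 0.7 are assumed; runs of 4,000 to 40,000 trials. The LOCF estimates match the arithmetic above. Two-sided type I error was:

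- about 6% in the waning case at 20% dropout, and 5.2% at the planned 10% (3.5% in favour of zoledronic acid against a nominal 2.5%);
- 5.2% to 5.6% in the declining case at 25% v 5%, and 5.1% at 15% v 5%. The Monte Carlo standard error at 4,000 trials is √(0.05 × 0.95 / 4,000), about 0.34 points, so small excesses over 5% in a short run mean little.

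A likelihood fit to the observed Month 6 and Month 12 values returned 0.63 at every dropout rate. It had about 0.6 points less power than LOCF at 10% dropout and 1.6 to 1.9 points less at 20%.

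**The case against.** The best defence is that the label is correct on the plan's own design. If placebo stays flat and zoledronic acid rises or holds after Month 6, LOCF is unbiased or pulls toward the null. The scenarios that favour the drug need waning despite a second infusion at Month 6, or a shared decline with unequal dropout. No section gives a Month 6 mean, a slope or dropout by arm. This stands, and it limits the size of the point. It rescues the label through an assumed trajectory, however, not through the reason given.

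Second, the carried value need not be a Month 6 scan after one infusion. Protocol 5.6.2, Section 6 and Table 6-1 call for the final-visit assessments, DXA included, at treatment discontinuation or early withdrawal. The last scan may therefore be later, or earlier. This also stands. The bias formula is unchanged, but any replacement model must say where such scans go, because the SAP applies no visit windows.

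Third, planned outputs show part of the picture: the Month 6 difference in the MITT set without imputation, Month 12 descriptive statistics and a plot over time. These help a reader judge whether the difference widened, but they do not supply an adjusted Month 12 estimate in the MITT set free of LOCF.

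Fourth, the likelihood fit recovers 0.63 partly by construction, because dropout in the simulation did not depend on outcome. Missing at random cannot be verified from the observed data. Both are true, but LOCF also rests on an untestable assumption, that nothing changes after the last scan.

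A reader might infer that LOCF inflates the drug effect or invalidates the primary test. The documents do not support that. At the planned dropout the shift is a few percent, and on the design values it is zero or toward the null.

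**Conclusion.** The stated reason for calling LOCF conservative is wrong for a Z-score endpoint, the direction of bias is not guaranteed, and no planned MITT analysis of the primary variable checks it. At 10% dropout the consequence is minor. The −4% figure rests on an assumed Month 6 difference of 0.40; across the tabulated trajectories the change runs from −5.0% to +2.7%. The larger figures (−7% to −11%, type I error near 6%) need 20% to 30% or strongly unequal dropout and are illustrations, not predictions. The arithmetic assumes that children who leave follow their arm's mean trajectory. That a Z-score is referenced to normal peers is its usual meaning and fits Protocol 3.6 and 9.8; the reference data are not described. The change is worth making because the Month 6 scans are already collected, not because the planned test is unsound.

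**What to change.** In Protocol 9.4.3 and the matching SAP section:

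- Make the primary analysis a repeated-measures model (MMRM) on observed Month 6 and Month 12 LS-BMD Z-score changes in the MITT set. Include treatment, visit, treatment-by-visit, pooled region, underlying condition, baseline Z-score and baseline-by-visit, with unstructured covariance. The Month 12 contrast is primary.
- Keep the LOCF ANCOVA as a sensitivity analysis in the same set.
- State to which visit a treatment-discontinuation or early-withdrawal DXA is assigned.
- Delete the growth-based sentence.
- Drop the zero-percent rule from the primary model. The MITT set already requires a post-baseline scan, so at most the rule could reach a child whose only such scan was at a discontinuation visit, where it would compete with LOCF. The visit-assignment rule covers that child.

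The cost is wording in two documents and one model, with no new data. The interval widens slightly (the power loss shown above), and the primary result then relies on missing at random, which the SAP should state openly.
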